**Categorization of Important Protocol Deviations**

Category	Sub-Category	Study Specific	Deviation Description	PPFLG	Methods of Identification
Study Procedures	Excluded Conmeds	Took prohibited conmed	13. Prohibited Conmed Therapy at any time during the trial	N	Edits and Monitoring
Study Procedures	Excluded Conmeds	Took pioglitzone 45 mg	14. Took Pioglitazone 45 mg at any time during the trial	Y	Edits and Monitoring
Eligibility	Inclusion/Exclusion	AHA therapy not stable	15. AHA Therapy not stable per protocol requirements prior to Visit 1	N	Monitoring
Eligibility	Inclusion/Exclusion	Diagnosed with other types of diabetes aside from T2DM	16. Diagnosed with T1DM or other types of diabetes aside from T2DM	Y	Monitoring
Eligibility	Inclusion/Exclusion	Liver disease	17. Have obvious clinical or radiographic signs/symptoms of liver disease (except nonalcoholic fatty liver disease), cirrhosis, acute or chronic hepatitis, or alanine aminotransferase (ALT/SGPT) and/or aspartate aminotransferase (AST/SGOT) levels $\geq 2.5X$ upper limit of normal (ULN), alkaline phosphatase $\geq 2X$ ULN or total bilirubin $\geq 2X$ ULN (with the exception of known Gilbert syndrome) as defined by central laboratory.	N	Monitoring and GLS data
Eligibility	Inclusion/Exclusion	Chronic kidney disease Stage 4 and higher	18. Have chronic kidney disease Stage 4 and higher (eGFR $< 30$ mL/min/1.73 m  ) or history of renal transplantation.	N	GLS data and monitoring

**Categorization of Important Protocol Deviations**

Category	Sub-Category	Study Specific	Deviation Description	PPFLG	Methods of Identification
Eligibility	Inclusion/Exclusion	History of more than 1 severe hypoglycemia episode	19. Have history of more than 1 episode of severe hypoglycemia requiring assistance of another person, resulting in coma, seizures, or disorientation within the 6 months prior to Visit 1.	N	CRF or monitoring
Eligibility	Inclusion/Exclusion	Received U-500R insulin by CSII	20. Have received U-500R insulin by CSII in the 3 months prior to Visit 1.	Y	CRF or monitoring
Eligibility	Inclusion/Exclusion	Had a blood transfusion or severe blood loss	21. Have had a blood transfusion or severe blood loss within 3 months prior to Visit 1 or have known hemoglobinopathy, hemolytic anemia, or sickle cell anemia that is known to interfere with HbA1c measurement.	Y	CRF or monitoring
Eligibility	Inclusion/Exclusion	Known allergy to human insulin preparations	22. Have known allergy to human insulin preparations or excipients contained in these products or prior history of suspected antibodies to human insulin.	N	Monitoring
Eligibility	Inclusion/Exclusion	Taking chronic systemic glucocorticoid therapy	23. Are taking chronic (lasting longer than 14 consecutive days) systemic glucocorticoid therapy (excluding topical, intra-articular, intraocular, and inhaled prescriptions), or have received any systemic glucocorticoid therapy within the 4 weeks immediately prior to Visit 1.	Y	CRF or monitoring

## Categorization of Important Protocol Deviations

Category	Sub-Category	Study Specific	Deviation Description	PPFLG	Methods of Identification
Eligibility	Inclusion/ Exclusion	Have an irregular sleep/wake cycle	24. Have an irregular sleep/wake cycle (for example, subjects who sleep during the day and work during the night), in the investigator's opinion.	N	Monitoring
Eligibility	Inclusion/ Exclusion	Intention to fasting	25. Intend to participate in an extended period of fasting during the study period (for religious or other purposes.)	N	Medical History; Monitoring
Eligibility	Inclusion/ Exclusion	Took prohibited conmed at entry	26. Have used rosiglitazone, sulfonylurea/glinides, pramlintide, once-weekly or twice-daily exenatide, or other AHAs not listed in the inclusion criteria in the 3 months prior to Visit 1 are taking AHA doses exceeding the respective product labels, or have a contraindication to current AHA usage per respective product labels.	N	CRF or monitoring
Eligibility	Inclusion/ Exclusion	Took weight loss drugs	27. Have used any weight loss drugs (for example, prescription drugs: lorcaserin, orlistat, phentermine, phentermine/topiramate, naltrexone/bupropion, or over-the-counter weight loss medications and herbal supplements) in the 3 months prior to Visit 1.	N	CRF or monitoring
Eligibility	Inclusion/ Exclusion	History of bariatric surgery	28. Have a history of bariatric surgery including Roux-en-Y gastric bypass surgery, gastric banding, and/or gastric sleeve.	Y	CRF or monitoring

**Categorization of Important Protocol Deviations**

Category	Sub-Category	Study Specific	Deviation Description	PPFLG	Methods of Identification
Eligibility	Inclusion/ Exclusion	History of malignancy	29. Have a history or an active or untreated malignancy, or in remission from a clinically important malignancy (other than basal cell or squamous cell skin cancer, in situ carcinomas of the cervix, colon or prostate that is considered cured) during the last 5 years before Visit 1 (if malignancy occurred >5 years ago, subject is eligible with documentation of disease-free state since treatment.)	N	CRF or monitoring
Eligibility	Inclusion/ Exclusion	Hearing loss and/or vision impairment	30. Important hearing loss and/or vision impairment deemed by the investigator to interfere with the safe use of the OmniPod U-500 System.	N	Monitoring
Eligibility	Inclusion/ Exclusion	Cardiac disease	31. Have cardiac disease with functional status that is Class III or IV according to the New York Heart Association Cardiac Disease Classification.	N	Monitoring

**Categorization of Important Protocol Deviations**

Category	Sub-Category	Study Specific	Deviation Description	PPFLG	Methods of Identification
Eligibility	Inclusion/ Exclusion	Breastfeeding or pregnant	32. Are women breastfeeding or pregnant or intend to become pregnant during the course of the study; are men who intend to impregnate their partners; or are sexually active of procreation potential not actively practicing birth control by a method determined by the investigator to be medically acceptable.	N	CRF or monitoring
Eligibility	Inclusion/ Exclusion	Investigator-site personnel and family	33. Are investigator-site personnel directly affiliated with this study and/or their immediate families. Immediate family is defined as spouse, parent, child, or sibling, whether biological or legally adopted.	N	Monitoring Source Documentation – should catch that all I/E were checked
Eligibility	Inclusion/ Exclusion	Lilly, Insulet, or TPO employee	34. Are Lilly or Insulet employees or are employees of third-party organizations (TPOs) involved in study who require exclusion of their employees.	N	Monitoring Source Documentation – should catch that all I/E were checked

**Categorization of Important Protocol Deviations**

Category	Sub-Category	Study Specific	Deviation Description	PPFLG	Methods of Identification
Eligibility	Inclusion/ Exclusion	Currently in any other clinical trials	35. Are currently enrolled in, or discontinued within the last 30 days, from a clinical trial involving an investigational product or non-approved use of a drug or device (other than the study treatment used in this study), or concurrently enrolled in any other type of medical research judged not to be scientifically or medically compatible with this study, and any subjects who have previously completed or withdrawn from this study.	Y	Summary or Monitoring Source Documentation – should catch that all I/E were checked
Eligibility	Inclusion/ Exclusion	Unwilling or unable to independently perform study procedures	36. Are unwilling or unable to independently perform study procedures, such as monitoring SMBG levels, recording diary data, and/or administering medication via syringe or CSII as applicable, or have any illness or condition (including known drug or alcohol abuse or psychiatric disorder) within the 6 months prior to Visit 1, that precludes subject from following and completing the protocol according to the investigator’s judgment. Subjects may not use a proxy to perform collection procedures, administer medication or record data.	N	Monitoring Source Documentation – should catch that all I/E were checked

**Categorization of Important Protocol Deviations**

Category	Sub-Category	Study Specific	Deviation Description	PPFLG	Methods of Identification
Study Procedures	Other	Missing HbA1c at V4 and/or V17	37. Missing primary efficacy measures at primary time point: specifically, missing HbA1c values at Visit 4 and/or Visit 17.	Y	GLS data and monitoring
Study Procedures	Other	Missing fasting plasma glucose (by laboratory measurement) at V4 and/or V17	38. Missing secondary efficacy measures at primary time point: specifically, missing fasting plasma glucose (FPG) values by laboratory measurement at Visit 4 and/or Visit 17.	N	GLS data
Study Procedures	Other	Random (as opposed to fasting) plasma glucose at V4 and/or V17	39. Fasting plasma glucose (by laboratory measurement) later determined to be a random draw at Visit 4 and/or Visit 17.	N	GLS data
Study Procedures	Visit Schedule Criteria	Missed office visit or visit window exceeds 3 weeks	40. Any missed office visit during the entire study or visit window intervals exceed 3 weeks outside of expected visit dates for in-office visits that significantly impacted the accuracy or reliability of the study data (does not include the allowable deviation time per study schedule).	N	Monitoring – Source Documentation
Study Procedures	Other	Subject continues study after pregnant	41. If the subject continues in the study after becoming pregnant post study enrollment.	N	Monitoring
Study Procedures	Violation of Discontinuation Criteria	Subject continues treatment after meeting DC criteria	42. Subject does not DC the study treatment or study while he/she should have DCd based on protocol criteria: Section 8.3.2 and Section 8.3.3 in study protocol.	Y	Monitoring
Study Procedures	Other	Subjects change AHA dose	43. Subject changes their dose of noninsulin pre-study AHA medications.	Y	InForm or Monitoring

## Categorization of Important Protocol Deviations

Category	Sub-Category	Study Specific	Deviation Description	PPFLG	Methods of Identification
Investigational Product	Treatment Assignment/ Randomization error	IWRS data entry errors that impact patient stratification	44. IWRS data entry errors that impact patient stratification (data entry error into IWRS- prior to randomization)	N	Check to match IWRS to visits
Safety	SAE	Failure to report SAE	45. Failure to report an SAE as required by protocol/GCP standards	N	Monitoring - Make sure SAEs are listed; Source documentation
Investigational Product	Other	Incorrect study treatment	46. Incorrect study treatment (post randomization) will be reviewed on a case by case basis (includes drug dispensing errors and failure to maintain their randomization treatment – CSII or MDI).	Y	Monitoring
Administrative/ Oversight	Suspected Misconduct	Suspected Fraud	47. Suspected Fraud	N	Monitoring
Administrative/ Oversight	Suspected Misconduct	Suspected Fraud	48. Confirmed Fraud	Y	Monitoring
Investigational Product	Other	Use of expired CT Material <7 days	49. Use of expired CT Material less than 7 consecutive days	N	Monitoring
Investigational Product	Other	Use of expired CT Material $\geq$ 7 days	50. Use of expired CT Material for at least 7 consecutive days	Y	Monitoring
Investigational Product	Patient took study drug not fit for use	Received drug that was declared “Not Fit for Use” <7 consecutive days	51. Subject received drug that was declared “Not Fit For Use” for less than 7 days	N	Monitoring
Investigational Product	Patient took study drug not fit for use	Received drug that was declared “Not Fit for Use” $\geq$ 7 consecutive days	52. Subject received drug that was declared “Not Fit for Use” for at least 7 consecutive days	Y	Monitoring
Administrative/ Oversight	Suspected Misconduct	Suspected scientific misconduct	53. Suspected Scientific misconduct	N	Monitoring

## Categorization of Important Protocol Deviations

Category	Sub-Category	Study Specific	Deviation Description	PPFLG	Methods of Identification
Administrative/ Oversight	Suspected Misconduct	Confirmed scientific misconduct	54. Only confirmed scientific misconduct will lead to exclusion from per-protocol population.	Y	Monitoring
Investigational Product	Compliance	Off study drug for >7 consecutive days	55. Subject off study drug for more than 7 consecutive days	Y	Monitoring
Investigational Product	Compliance	Subject <80% compliant with algorithm	56. If the investigator determines that that patient is noncompliant (<80% compliant with algorithm) and should be discontinued.	Y	Monitoring
Study Procedures	Other	Lack of initiation of rescue therapy	57. Lack of initiation of rescue therapy despite meeting rescue criteria.	N	Monitoring
Study Procedures	Other	Inappropriate rescue	58. Inappropriate rescue despite not meeting rescue criteria.	Y	Monitoring; Source Documents
Investigational Product	Compliance	Took more than the prescribed study treatment	59. Is judged by the investigator to have intentionally or repeatedly taken more or less than the prescribed amount of medication that may cause patient safety concerns.	N	Monitoring
Study Procedures	Other	Other, Not specified	60. Other, not specified (i.e. delay in randomization, investigator used PI discretion vs. titration tools, staff member not listed on 1572, site did not use IWRS to dispense medication or Pod, dosing error)	N	Monitoring
Eligibility	Inclusion/Exclusion	Subject switched to U-500R prior to V4	61. Subject did not continue their pre-study insulin regimen until Visit 4; subject switched from their baseline insulin to U-500R at Visit 1	Y	Monitoring

**Categorization of Important Protocol Deviations (Abbreviations)**

Abbreviations: AHA = antihyperglycemic agents; BMI = body mass index; Conmed = concomitant medication; CGM = continuous glucose monitoring; CRF = case report form; CSII = continuous subcutaneous insulin infusion; DC = discontinue; DCd = discontinued; GLS = Generic Laboratory System; HbA1c = hemoglobin A1c; ICD = informed consent document; I/E = inclusion/exclusion; IWRS = Interactive Web Response System; MDI = multiple daily injections; N = no; NA = not applicable; PPFLG = per-protocol population exclusion flag; SAE = serious adverse event; SGOT = serum glutamic oxaloacetic transaminase; SGPT = serum glutamic pyruvic transaminase; SMBG = self-monitored blood glucose; T1DM = type 1 diabetes mellitus; T2DM = type 2 diabetes mellitus; TDD = total daily dose; ULN = upper limit of normal; V = visit; Y = yes.

## 5.9. Primary Outcome and Methodology

The primary efficacy measure is change from baseline to the 26-week HbA1c value. The primary analysis will be conducted for the ARS population in Group A. There will be 2 primary analysis methods for different purposes as follows.

1. Per FDA's request, the analysis method will use the copy reference approach to impute missing data based on multiple imputations with a pattern mixture model (later referred to as 'copy reference multiple imputation analysis'). This analysis will include post study treatment discontinuation data. The reference is all observed data from all randomized subjects in the U-500R MDI arm who discontinued study treatment but completed the study without missing data. After imputation, an ANCOVA with baseline HbA1c as a covariate, treatment (U-500R CSII, U-500R MDI) and the stratification factor (U-500R at entry versus other insulins) as fixed effects will be used to analyze the 26-week HbA1c including imputed values.

If in the reference group mentioned above there is only a limited number of subjects and this leads to a failure in performing the proposed multiple imputation analysis, the reference will be changed to include all observed data from all randomized subjects in the U-500R MDI arm who do not have missing data.

2. For manuscripts and other non-FDA submission purposes, an MMRM model that does not include post study treatment discontinuation data and adjusts for missing data through an observed-data-likelihood-based approach will be used. The model will include the following fixed effects: treatment (U-500R CSII, U-500R MDI), weeks on treatment, the interaction between treatment and weeks, and the stratification factor (U-500R at entry versus other insulins). The model will also include baseline HbA1c as a covariate.

As a sensitivity analysis to the missing at random assumption of MMRM model, a stress test will be performed. The missing data are first imputed with the missing at random assumption. Prior to multiple-imputation analysis, in the CSII arm the imputed values will be replaced by the imputed value plus delta. Multiple values of delta within a clinically reasonable and meaningful range will be tested (delta=0.1, 0.2, 0.3, 0.4) to assess if the conclusion from the MMRM primary analysis changes.

For the MMRM model, the Kenward-Roger approximation will be used to estimate denominator degrees of freedom. An unstructured covariance matrix will be used to model the within-subject errors. If the unstructured covariance configuration results in a lack of convergence, then the following variance-covariance matrix will be used (in order) until one converges:

Heterogeneous Toeplitz; Heterogeneous First Order Autoregressive; Heterogeneous Compound Symmetry; Toeplitz; First Order Autoregressive; Compound Symmetry. If all variance-covariance matrices selected fail to converge, Variance Components will be used as the next attempt at convergence.

The test for the primary objective of non-inferiority will be performed at the 0.05 significance level using the LSMean estimate of the difference in change in HbA1c between the 2 treatments

at Week 26. Non-inferiority will be established if the upper limit of a 2-sided 95% confidence interval (CI) for the difference (U-500R CSII minus U-500R MDI) is below the NIM of 0.4%.

Using the LSMean estimate of the difference in change in HbA1c between the 2 treatments, superiority will be established if the upper limit of a 2-sided 95% CI for the difference (U-500R CSII minus U-500R MDI) is below 0.

The following supportive and sensitivity analyses will also be conducted:

- If the following sets are different from ARS, then similar copy reference multiple imputation and MMRM analyses will be done for the FAS (subjects who were randomized and received at least 1 dose of the study insulin through the administration method they were assigned to), all completer set (subjects who complete the study treatment), and the per-protocol population (subjects included in the ARS who have completed the study without important protocol deviations that will impact the primary outcome).
- An ANCOVA model with similar fixed effects as in the copy reference multiple imputation analysis using LOCF method for the ARS will also be performed.
- For the analysis performed for the ARS population for Groups A+B, the analysis model will include an additional stratification factor (nonusers versus users of GLP-1 receptor agonists or SGLT2 inhibitors) as a fixed effect.

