9.9. Special Treatment Considerations

9.9.1. Rescue Therapy

Rescue therapy should be initiated in the following circumstances:

- If median of 3 fasting SMBG >300 mg/dL over a 3-day period is unexplained from previous week, starting at Visit 10 through Visit 13 (Weeks 8 through 14).
- If HbA1c value at Visit 13 (Week 14) is ≥10.0% and decreased by <0.4% compared to Visit 10 (Week 8) HbA1c.
- If HbA1c value at Visit 15 (Week 20) is ≥10.0% and decreased by <0.4% compared to Visit 13 (Week 14) HbA1c.

Subjects receiving U-500R MDI will be rescued by the addition of a bedtime U-500R dose (increase injections to 4-times daily therapy). A suggested starting dose for the rescue dose would be 10% of TDD, but this may be modified based on investigator judgment.

Subjects receiving CSII U-500R will be rescued by the addition of a bedtime U-500R dose delivered by CSII. A suggested starting dose for the rescue dose would be 5% to 10% of TDD, but this may be modified based on investigator judgment.

Subjects should be instructed to record their 0300-hour BG within 24 hours after adding a rescue dose and subjects should also be encouraged to record their 0300-hour BG 2 to 3 times the first 2 weeks after adding a rescue dose.

Every attempt should be made to keep these subjects in the study. Change in treatment regimen should be recorded in the eCRF.

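### The non-FDA primary MMRM fits one baseline HbA1c slope to all four visits; adding baseline-by-week removes a possible bias at Week 26 at almost no cost

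*SAP*

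**What the plan says.** SAP 5.9 has two primary methods, both applied to all randomized subjects in Group A. The FDA method imputes missing values and then fits an ANCOVA that "will be used to analyze the 26-week HbA1c including imputed values". It models Week 26 only.

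The second method is introduced this way: "For manuscripts and other non-FDA submission purposes, an MMRM model that does not include post study treatment discontinuation data". Its fixed effects are treatment, "weeks on treatment, the interaction between treatment and weeks, and the stratification factor (U-500R at entry versus other insulins"). Then: "The model will also include baseline HbA1c as a covariate". Protocol 12.2.7 and the Protocol synopsis give the same model. The covariance is left free at first: "An unstructured covariance matrix will be used to model the within-subject errors". The baseline slope is not left free.

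HbA1c is measured after baseline at Weeks 8, 14, 20 and 26 (Protocol Attachment 1). The rescue rules in Protocol 9.9.1 use the same visits: "compared to Visit 10 (Week 8) HbA1c" and "If HbA1c value at Visit 15 (Week 20) is". Noninferiority is declared when the upper limit of the two-sided 95% interval for CSII minus MDI at Week 26 "is below the NIM of 0.4" percentage points.

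**The concern.** An MMRM handles missing Week 26 values by predicting them, in effect, from the subject's baseline and earlier visits. That is valid under missing at random only if the mean model is right at Week 26. A common slope is a compromise over four visits. If the true slope at Week 26 differs from it, and subjects without Week 26 data differ in baseline by arm, the error does not cancel between arms.

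The design makes a changing slope plausible. Starting dose conversion depends on screening HbA1c for most subjects (Protocol 9.7). Dose steps grow with glucose level, toward one target range (Protocol 9.8.1.1 and 9.8.2.1). Intensive titration runs from Week 2 to Week 14, so Week 8 falls in the middle of it.

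Arm-specific loss is plausible too. The trial is open-label, 25% dropout is assumed, and this MMRM also drops data after treatment discontinuation. Discontinuation can follow from poor adherence to titration algorithms that differ by arm (Protocol 8.3.2).

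At stake is a shift in a primary noninferiority estimate. It could go toward false noninferiority or toward lost power.

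**Working it through.** **The plan's own figure.** The sample size gives n per arm = 2(1.960 + 0.842)² × 1.1² / 0.4² = 118.7, so 119 per arm and 238 in total, against 240 completers stated. 240 / 0.75 = 320 randomized. This is reproduced, and the point below does not touch it.

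**Inputs.** From the documents: four visits, about 160 per arm, about 25% dropout, margin 0.4. Assumed, because the documents give nothing: baseline SD 1.0, residual SD 1.0, correlations between visits of 0.55 to 0.75, slopes of change on baseline by visit, and the log-odds of dropout per 1% of baseline HbA1c in each arm. With a slope of -0.5 these imply an SD of change of √(1.0² + 0.5² × 1.0²) = 1.12, in line with the SAP's 1.1.

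**Hand check of sign and size.** Bias ≈ (Week 26 slope − common slope) × (completers' mean baseline, CSII − MDI). For slopes -0.30, -0.40, -0.50, -0.55 the plain average is -0.4375, so the gap is -0.1125. If only CSII loses high-baseline subjects (log-odds 0.7), the completers' baseline difference is -0.19 and the bias is about +0.021. With opposite dropout (0.7 and -0.7) the difference is -0.38 and the bias about +0.043. The simulated values are 0.025 and 0.046. For steeper slopes the hand figure falls further short, because the fitted common slope is not a plain average and misfit at earlier visits also enters through the correlation.

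**Large-sample bias** (60,000 per arm, unstructured covariance, maximum likelihood, simulation error 0.006 to 0.007):

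| Slopes, Weeks 8 to 26 | Dropout log-odds, CSII / MDI | Common slope | Baseline-by-week |
|---|---|---|---|
| -0.30 to -0.55 | 0.7 / 0.7 | -0.010 | -0.009 |
| -0.30 to -0.55 | 0.7 / 0 | 0.025 | -0.001 |
| -0.30 to -0.55 | 0.7 / -0.7 | 0.046 | -0.010 |
| -0.30 to -0.55 | 1.1 / -1.1 | 0.082 | 0.000 |
| -0.20 to -0.60 | 0 / 0 | 0.001 | 0.001 |
| -0.20 to -0.60 | 0.7 / 0 | 0.051 | 0.009 |
| -0.20 to -0.60 | 0.7 / -0.7 | 0.083 | 0.000 |
| -0.20 to -0.60 | 1.1 / -1.1 | 0.127 | 0.005 |

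A separate simulation used slopes of -0.35 to -0.55 and -0.20 to -0.65, correlation 0.7, and dropout related to baseline in CSII only. It gave 0.01 to 0.04 in either direction with the common slope and at most 0.003 with baseline-by-week. A further run gave 0.02 to 0.05 for one-arm dropout and up to 0.11 for opposite dropout with steep slopes.

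**Trial size** (160 per arm, 2,000 trials, true difference 0.4, nominal one-sided error 0.025, simulation error about 0.004, no Kenward-Roger correction):

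| Slopes | Dropout log-odds, CSII / MDI | Bias, common | Type I error, common | Type I error, by-week |
|---|---|---|---|---|
| constant -0.5 | -0.7 / 0.7 | -0.003 | 0.029 | 0.030 |
| -0.20 to -0.60 | 0.7 / 0.7 | -0.001 | 0.026 | 0.024 |
| -0.30 to -0.55 | 0 / 0.7 | -0.029 | 0.051 | 0.033 |
| -0.30 to -0.55 | -0.7 / 0.7 | -0.056 | 0.078 | 0.030 |
| -0.20 to -0.60 | -0.7 / 0.7 | -0.084 | 0.112 | 0.030 |

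In the reverse direction (slopes -0.30 to -0.55, log-odds 0.7 / -0.7) the bias was +0.052. Power at a true difference of 0 was then 0.798, against 0.889 with baseline-by-week.

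**Cost of the extra term.** Mean SE was 0.123 to 0.127 under both models, never more than 0.002 higher with baseline-by-week. When slopes were truly equal and dropout extreme, power was 0.875 against 0.888.

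**The case against.** The strongest reply is that the bias is hypothetical. Neither document gives a slope by visit, and the only dropout figure is 25% overall, not split by arm or baseline. Every bias figure here rests on assumed inputs. That stands, and it makes this a risk to remove, not an error shown.

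Second, differential dropout alone does no harm. A reader might infer that it biases the MMRM by itself. It does not: with a constant slope, even opposite dropout gave no bias.

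Third, the FDA analysis is not exposed. A reader might infer that every primary result is in doubt, but the ANCOVA estimates its own Week 26 slope. It is no substitute for a sound MMRM, though, because it includes data after treatment discontinuation and so estimates a different quantity.

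Fourth, the delta stress test adds up to 0.4 to imputed CSII values. With 25% imputed, that moves the CSII mean by 0.25 × 0.4 = 0.10, as large as most of the biases above and in the direction that guards against false noninferiority. This stands as partial protection. But the test does not free the slope, does not correct the reported estimate and does not address lost power. The SAP also does not specify the imputation model behind it.

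**Conclusion.** The point holds as a cheap improvement to the non-FDA primary MMRM. As written, one slope covers four visits. If the slope changes over the weeks and loss of data depends on baseline differently by arm, the Week 26 difference is biased. One-arm dropout gives about 0.01 to 0.05 percentage points, or 2.5% to 12.5% of the 0.4 margin. Opposite dropout gives about 0.05 to 0.11, reaching 0.13 in the most extreme setting tried. The sign follows which arm loses high-baseline subjects.

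These sizes depend on the assumed slopes, dropout relations, SDs and correlations. The documents do not support saying that the slope does steepen, that the trial's result is biased, or that the FDA analysis is affected. Nor is a general precision gain a reason for the change: the two models' standard errors were nearly equal in the trial-size runs. The sample size is unaffected.

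**What to change.** Before database lock, while the study team is still blinded to aggregate data (SAP 6.1), add baseline HbA1c-by-week to the MMRM in SAP 5.9. Align the Protocol synopsis and Protocol 12.2.7. If the sponsor judges that no principal feature changes, Protocol 12.2.1 lets the change and its reason be recorded in the clinical study report instead.

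The cost is three extra parameters, an SE increase of about 0.002 or less, and at most about 1 point of power if the slopes are truly equal.

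A matching term in the secondary MMRMs (SAP 5.10) is optional and was not simulated. It needs one extra parameter each for FPG and 7-point SMBG, which have only Weeks 14 and 26 after baseline, and more for total daily dose.
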